### **11.2. DIARY CARD**

Diary Cards will be supplied by the CRO appointed by Dompé. They are the sole property of Dompé and should not be made available in any form to third parties, except for authorized Dompé's designee or representatives of appropriate Health/Regulatory Authorities, without written permission from Dompé.

A sample Diary Cards is provided in **Appendix 14.7**. Translation into a language different from English, will be provided, if required.

Diary Cards are required and should be completed for each patient. It is responsibility of the Investigator to explain to each patient how to enter the data in the Diary Card.

### **11.3. DATA MANAGEMENT**

Data management of the CRFs and Diary Cards will be performed by the CRO appointed by Dompé.

The CRF and Diary Card pages for all patients will be data-entered (double data entry) into the study database, and the data will be verified for missing data, inconsistencies, and for any necessary medical clarifications. Queries arising from these checks will be sent to the Investigator for response and signature.

Once all data queries have been resolved, the study will be declared to be "clean", and the study data will be locked ready for analysis.

After the database lock has been achieved, the Investigator may archive the copies of the CRFs and Diary Card retained at the centre. The original CRF and Diary Card collected by the CRO appointed by Dompé will be transferred to Dompé for archiving.

### **11.4. DOCUMENTATION REQUIRED PRIOR TO INITIATION OF AND DURING THE STUDY**

In addition to the documents mentioned in **Sections 10.1** and **12.1**, the following will be required from the Investigator prior to the initiation visit:

- Current, signed and dated Curriculum Vitae, GCP qualification, and Financial Disclosure Statement of Principal Investigator and any Sub-Investigators. Updates should be provided at least every two years.

- Normal ranges of all laboratory tests to be performed at the study site and a recent certification or accreditation of established quality control (or other documentation of established quality control or external quality assessment or other validation). Updates should be provided as soon as any reference value has changed.
- A signed page of the final protocol and any amendments.
- A signed original of the study Financial Agreement/Clinical Study Agreement with Dompé, including Pharmacy, laboratory etc (i.e. all study specific costs).
- List and any updates of delegated responsibility (Study Team Signature List / Delegation of Responsibilities form).
- Form 1572 and financial disclosure form 3455 from all the persons listed on the 1572.

### **11.5. ESSENTIAL DOCUMENT RETENTION**

The Investigator will retain copies of all the essential documents (as defined by ICH-GCP) until at least 2 years after the last approval of a marketing application in an ICH region, and until there are no pending or contemplated marketing applications in an ICH region, or at least 2 years have elapsed since the formal discontinuation of clinical development of the Investigational Product. These documents should be retained for a longer period however if required by the applicable regulatory requirements. The Investigator should take measures to prevent accidental or premature destruction of these documents.

The essential documents include at least: the signed protocol, copies of the completed CRFs, and Diary Cards, signed Patient Informed Consent Forms from all patients who consented, hospital records and other source documents, and all other documentation included in the Investigator Site File and Pharmacy/Dispensing File.

The Investigator will inform Dompé of the storage location of these essential documents and must contact Dompé before disposing of any. If the Investigator wishes to assign the files to someone else or to remove them to another location, he/she should consult with Dompé about this change.

Dompé will inform the Investigator in writing when these documents no longer need to be retained.

## **12. STUDY MANAGEMENT**

The study will be performed in accordance with the protocol, the Declaration of Helsinki (59th WMA General Assembly, Seoul, October 2008) and ICH Harmonised Tripartite Guideline for Good Clinical Practice (*ICH-GCP*) and any local regulations.

### **12.1. REGULATORY BODY APPROVAL**

The study will not be started until review from FDA has been positively completed.

### **12.2. STAFF INFORMATION & RESPONSIBILITIES**

It is the responsibility of the Investigator to ensure that all personnel involved in the study are fully informed of all relevant aspects of the study, including detailed knowledge of and training in all procedures to be followed.

The Investigator will provide a list of delegated responsibility to the CRO appointed by Dompé detailing the various study tasks to be performed by each member of his/her study staff. Each staff member should sign in agreement to their performing each of the tasks delegated to them on the list.

### **12.3. MONITORING**

Monitoring will be carried out by CRAs of the CRO appointed by Dompé.

Prior to study start, the Investigator will be informed of the anticipated frequency of the monitoring visits. (S)He will also receive a notification prior to each monitoring visit during the course of the study. It is expected that the Investigator and/or his/her sub-Investigator(s) and other appropriate staff will be available on the day of the visit to discuss study conduct and to cooperate with the monitor to ensure that any problems detected during the course of these monitoring visits are resolved.

The purpose of the monitoring visit is to verify that the rights and the wellbeing of the patient are protected, that the reported data are accurate, complete and verifiable from source documents and that the conduct of the trial complies with the currently approved protocol and any amendments, with ICH GCP, and with regulatory requirements.

Monitoring at the Pharmacy will be carried out by the U-CRA in order to maintain study blind with all other CRO/site staff involved.

#### **12.3.1. Access to records**

The Investigator will allow designated Dompé representatives and regulatory bodies to have direct access to the source documents to verify the data reported in the CRFs. Source documents are the originals of any documents used by the Investigator or hospital/institution that allow verification of the existence of the patient and substantiate the integrity of the data collected during the trial. Source documents should be available to support all the data recorded in the CRF. Location of source data, including those for which the CRF might be accepted as being the sole source document, will be specified and listed at the centre Initiation Visit.

### **12.4. AUDIT AND INSPECTION**

Audit activities will be performed by the Quality Assurance of the CRO appointed by Dompé, except for audit to Protocol/Amendments, Patient Informed Consent Document (template) and CRF that will be done by the Dompé Quality Assurance Unit.

On one or more occasions the study site may be audited by the CRO appointed by Dompé. The Investigator will be informed in advance of such a visit.

Additionally the study site may be inspected by a regulatory agency on one or more occasions.

## **12.5. DATA MONITORING COMMITTEE**

An independent Data Monitoring Committee (DMC) will be established and will be responsible for safeguarding the interests of trial participants, and for enhancing the integrity and credibility of the trial. The DMC will assess the safety and efficacy of the interventions during the trial, and will monitor the overall conduct of the clinical trial. The DMC will provide recommendations to Dompé about stopping or continuing the trial. To contribute to enhancing the integrity of the trial, the DMC may also formulate recommendations to Dompé relating to the selection/recruitment/retention of participants, their management, improving adherence to protocol-specified regimens and retention of participants, and the procedures for data management and quality control.

The DMC will operate independently of Dompé, and its members will not have connections to Dompé with the exception of the compensation to DMC members related to their activities.

The DMC will comprise three members. They will be a multidisciplinary group that will include:

- Two surgeons/physicians with extensive experience in islet transplantation and critical care medicine (e.g. a Medical Director of a Transplant Program);
- A Biostatistician with substantial experience in the DMC process.

The DMC:

- Will review unblinded data. To this purpose, an Independent Statistician will liaise with the CRO statistician and will have access to those components of the database necessary to generate the reports to the DMC.
- Will be responsible for the ongoing (at least every 4 months) review of safety data throughout the trial. Primary among the safety data that will be reviewed are Serious AEs. In particular, the DMC will monitor the number of deaths for both arms of the study to assess whether mortality is consistent with historical data. The DMC also will give attention to post-surgical reoperation and clinically significant coagulation abnormalities (intra-abdominal as well as gastrointestinal hemorrhage have been reported to be the most common reasons for reoperation).
- Will review efficacy data in an ongoing manner to enable the assessment of the acceptability of safety in the context of emerging evidence about efficacy, i.e. measures of metabolic control and graft function.
- Will be advisory to Dompé and make recommendations to Dompé regarding the continuation of the trial and potential modifications to the design and conduct of the trial. These recommendations will be made in a manner to maintain confidentiality of emerging information about efficacy and safety, unless access to certain data is needed to enable Dompé to make decisions about the DMC recommendations. Dompé will be responsible for promptly reviewing the DMC recommendations, to decide whether to continue or terminate the trial, and to determine whether amendments to the protocol or changes in the study conduct are required

All details of the conduct and responsibilities of the DMC will comply with Guidance for Clinical Trial Sponsors: Establishment and Operation of Clinical Trial Data Monitoring Committees and will be described in the 'DMC Charter' to be finalized during the set-up phase of the study and prior to the initiation of enrollment.

## **12.6. PROTOCOL DEVIATIONS/AMENDMENTS**

Changes to the Protocol will be implemented only when written amendments have been signed by all individuals who signed the protocol.

Any amendment will be sent to the appropriate IRB. No deviations from or changes to the protocol will be implemented without documented approval of an amendment from the IRB which granted the original approval, except where necessary to eliminate an immediate hazard(s) to trial patient, or when the change(s) involves only logistical or administrative aspects of the trial. The deviations from or changes to the protocol implemented to eliminate an immediate hazard to the trial patient and the proposed amendment, if appropriate, should be submitted to the IRB for review and approval as soon as possible.

Any other deviation from the protocol that has not been approved by Dompé and the IRB could result in a discontinuation from the study at the centre involved.

Any written amendment will be sent to all recipients of the protocol and to the Competent Authorities.

## **12.7. DISCONTINUATION OF THE STUDY**

Dompé reserves the right to stop the study at any time on the basis of new information regarding safety or efficacy, or if study progress is unsatisfactory, or for other valid administrative reasons.

After such a decision is made, the Investigator must inform all relevant persons e.g. study staff, potential patients etc. within 2 weeks. All delivered study materials must be collected and all CRFs completed to the extent possible.

Study discontinuation will be notified to the FDA within 5 days from decision.

## **12.8. PUBLICATIONS**

As this study is part of a multicentre trial, publications derived from this study will be planned and agreed with the participating Investigators. Publications will include input from the Investigators, his/her colleagues, other investigators in this trial and Dompé personnel. Such input will be reflected in publication authorship. Criteria for selection of authors will be agreed. Subsequent to the multicentre publication or one year after completion of the study, whichever occurs first, an Investigator and/or his/her colleagues may publish the results of Investigator's part of the study independently.

Any manuscript, abstract or other publication or presentation of results or information arising in connection with the study must be prepared in conjunction with Dompé and must be submitted to the Dompé for review and comment at least 45 days prior to submission for publication or presentation. If such draft contains confidential patentable information, the Investigator will refrain from publishing any such information for a period not exceeding 180 days, to enable Dompé to file for the protection of any intellectual or proprietary property interest.

## 14. APPENDICES

### 14.1. APPENDIX 1 – CUMULATIVE SUMMARY OF ADVERSE DRUG REACTIONS

MedDRA Body System / LLT	Non Serious	Serious	Frequency
Blood and lymphatic system disorders	3	1	4.30%
Anaemia	2		
Coagulopathy		1	
Lymphadenopathy	1		
Cardiac Disorders	1	0	1.08%
Tachycardia	1		
Gastrointestinal Disorders	13	0	13.98%
Abdominal pain NOS	1		
Dyspepsia	1		
Flatulence	2		
Gastroesophageal reflux disease	1		
Nausea	6		
Vomiting	2		
General disorders and administration site conditions	21	0	22.58%
Canula site reaction	13		
Fatigue	1		
Injection site thrombosis	3		
Infusion site oedema	2		
Lethargy	1		
Oedema peripheral	1		
Immune system disorders	0	1	1.08%
Lung transplant rejection		1	
Injury, poisoning and procedural complications	1	0	1.08%
Complications of transplanted kidney	1		
Investigations	2	0	2.15%
Blood amylase increased	1		
Liver function test abnormal	1		
Metabolic and nutrition disorders	1	0	1.08%
Hyperkalaemia	1		
Musculoskeletal and connective tissue disorders	1	0	1.08%
Arthralgia	1		
Nervous system disorders	25	0	26.88%
Dizziness	3		
Headache	8		
Hypoesthesia	3		
Somnolence	11		
Psychiatric disorders	4	0	4.30%

Adverse Drug Reactions - Number of Reports by Terms			Frequency
MedDRA Body System / LLT	Non Serious	Serious	
Abnormal dream	1		
Restlessness	1		
Euphoric mood	2		
Renal and urinary disorders	4	0	4.30%
Renal failure	1		
Renal tubular necrosis	2		
Urinary retention	1		
Respiratory, thoracic and mediastinal disorders	6	1	7.53%
Bradypnoea	1		
Cough	2		
Nasopharyngitis	2		
Respiratory failure		1	
Sore throat	1		
Skin and subcutaneous system disorders	4	0	4.30%
Erythema	1		
Infusion site erythema	2		
Pruritis	1		
Vascular disorders	1	3	4.30%
Haemorrhage		1	
Hypotension	1		
Retroperitoneal haemorrhage		2	
TOTAL	87	6	

1 = table does not include ADRs reported from the ongoing pilot trial in islet allo-transplant patients

The most frequent (>10%) ADRs observed in the phase 1 and phase 2 studies were:

Nervous system disorders (about 27%), including headache, dizziness, hypoaesthesia, somnolence.

## 14.2. APPENDIX 2 - PACKAGING AND LABELING DETAILS

The template of label specimens is provided below.

### Specimen label for the REPARIXIN Vial

STUDY REP0112	Sponsor Dompé s.p.a.; [name] Phone: [name]	
REPARIXIN		
INVESTIGATOR:		
CONTAINS: 250 mL REPARIXIN (33 mg/mL) CONCENTRATE FOR SOLUTION FOR I.V. INFUSION		
BATCH No.	EXPIRY DATE mm/yyyy	DO NOT STORE AT >30°C (86°F)
DIRECTIONS: Transfer into an INFUSION BAG the content of the vial + 500 mL of 0.9% NaCl, according to procedures detailed in the "Instructions to the Pharmacy".		
Caution: New Drug-Limited by Federal law to investigational use.		

### Specimen label for the PLACEBO Vial

STUDY REP0112	Sponsor Dompé s.p.a.; [name] Phone: [name]	
PLACEBO		
INVESTIGATOR:		
CONTAINS: 250 mL Physiologic salt solution (0.9% w/v sodium chloride)		
BATCH No.	EXPIRY DATE mm/yyyy	DO NOT STORE AT >30°C (86°F)
DIRECTIONS: Transfer into an INFUSION BAG the content of the vial + 500 mL of 0.9% NaCl, according to procedures detailed in the "Instructions to the Pharmacy".		
Caution: New Drug-Limited by Federal law to investigational use.		

**Specimen label for Infusion Bag - “double tear off” label**

Each of the 2 sections of the double label will have identical information as per specimen below.

STUDY REP0112		Sponsor Dompé s.p.a.; [name] Phone: [name]	
PATIENT No.    		INFUSION BAG No. 	
INVESTIGATOR:			
CONTAINS: 750 mL OF REPARIXIN (11.00 mg/mL) or PLACEBO I.V. INJECTABLE DOSING SOLUTION			
PREPARED ON       /       /          :       dd / mm / yyyy : hh : mm		DO NOT STORE AT >30°C (86°F)	
USE BY       /       /          :       dd / mm / yyyy : hh : mm			
DIRECTIONS: Administer as a continuous i.v. infusion into a (high flow) central vein, by an infusion pump. Infusion will start approximately 12 hours (6 to 18) before islet infusion. Pump rate will be adjusted according to patient body weight as per Appendix 3 of Study Protocol.			
Caution: New Drug-Limited by Federal law to investigational use.			

**NOTE:** Shadowed field are those to be completed by the pharmacist at the time of preparation.

Patient No. Report the four digit number derived from the “IP Preparation Order Form” received from the Investigator.

Infusion Bag No. Report the sequential bag number within the series for that patient.

Preparation date/time Report the date and time when the preparation of the dosing solution has started.

Use by date/time Calculate the use by date and time as date/time of preparation + maximum 72 hours (expiry date/time of the dosing solution), unless the site has more restrictive rules for reconstituted solutions (e.g. 24 hours).

**14.3. APPENDIX 3 - STUDY DRUG INFUSION RATE BY BODY WEIGHT**

Reparixin dose = 2.772 mg/kg/hour for 7 days (168 hours)

Dosing solution = 11 mg/mL

BODY WEIGHT(kg) each figure is from 0.00 to 0.99	INFUSION RATE (mL/hour)	24 hours INFUSION VOLUME (mL)
45	11.3	271.2
46	11.6	278.4
47	11.8	283.2
48	12.1	290.4
49	12.3	295.2
50	12.6	302.4
51	12.9	309.6
52	13.1	314.4
53	13.4	321.6
54	13.6	326.4
55	13.9	333.6
56	14.1	338.4
57	14.4	345.6
58	14.6	350.4
59	14.9	357.6
60	15.1	362.4
61	15.4	369.6
62	15.6	374.4
63	15.9	381.6
64	16.1	386.4
65	16.4	393.6
66	16.6	398.4
67	16.9	405.6
68	17.1	410.4
69	17.4	417.6
70	17.6	422.4
71	17.9	429.6
72	18.1	434.4
73	18.4	441.6

BODY WEIGHT(kg) each figure is from 0.00 to 0.99	INFUSION RATE (mL/hour)	24 hours INFUSION VOLUME (mL)
74	18.6	446.4
75	18.9	453.6
76	19.2	460.8
77	19.4	465.6
78	19.7	472.8
79	19.9	477.6
80	20.2	484.8
81	20.4	489.6
82	20.7	496.8
83	20.9	501.6
84	21.2	508.8
85	21.4	513.6
86	21.7	520.8
87	21.9	525.6
88	22.2	532.8
89	22.4	537.6
90	22.7	544.8
91	22.9	549.6
92	23.2	556.8
93	23.4	561.6
94	23.7	568.8
95	23.9	573.6
96	24.2	580.8
97	24.4	585.6
98	24.7	592.8
99	24.9	597.6
100	25.2	604.8

## 14.4. APPENDIX 4 - STUDY FLOW CHART

Test/Examination	HOSPITAL STAY											FOLLOW-UP	
	Screening	day -1	day 0 Tx day	day 1	day 2	day 3	day 4	day 5	day 6	day 7	Hospital discharge	day 75±14 post transplant	day 365±14 post transplant
Informed consent	X												
Inclusion/exclusion criteria	X												
BP, HR, weight, height 	X										X 	X 	X 
Safety laboratory tests	X										X		
Pregnancy test	X												
Renal reserve/function  & Total bilirubin	X		X	X	X	X	X	X					
Albumin and pre-albumin	X											X	X
Concurrent sepsis	X												
Pre-operative portal hypertension	X												
miR-375; Inflammatory chemokines/cytokines 	XX 	XXX 	X 		X 		X 		X 				
Study drug administration 		X-----								X-----			
PK sampling 			X		X		X		X		X 		
ALT/AST			X	X	X	X	X	X	X	X		X	
XDP, INR/PTT, CRP			X	X	X	X	X	X	X	X			
Average daily insulin; HbA1c												X	X
Severe, Documented Symptomatic, Asymptomatic hyperglycemia events												X-----	X
MMTT  ; Glucose, C-peptide, insulin												X	X
β-score – TEF calculation												X	X
Steatorrhea  and malnutrition risk 												X	X
Adverse Events		X-----									Record all AEs up to each hospital discharge Then, only SAEs -----X		
Concomitant Medication	X-----	Record all CMEDs up to each hospital discharge Then, only drugs used for SAEs, oral hypoglycemic drugs and forbidden medications -----X											

1 = Measure only BP and HR at hospital discharge. Measure only weight at follow-up visits.

2 = Assess Creatinine clearance on pre-transplant. Assess creatinine clearance AND urine output from day 1 to day 6 post-transplant.

3 = Store a serum sample for centralized assay as detailed in **Appendix 14.6.3**. Take the 2 chemokines/cytokines pre-transplant samples 6 to 24 hours apart; obtain all basal samples before surgery and before the Investigational Product administration is started. Take post-transplant samples @ 6, 12, 24, 72, 120 and 168hrs after islet infusion.

4 = Start study drug infusion approximately 12 (6-18) hours before islet infusion. Obtain PK ideally in the morning (day 1, 3, 5 post-transplant). Obtain (if you are one of the 2 selected sites) a sample just prior to, and then 1, 3, 5, 6, 8, and 12 hours after the end of study drug administration.

5= Mixed Meal Tolerance Test: measure glucose, C-peptide and insulin prior to (2 basal samples in the range between -20 to 0 prior to the meal) AND @ 15, 30, 60, 90, 120, 180 and 240 min after the meal, as detailed in **Appendix 14.6.4**. Store a blood sample for centralized assay of C-peptide and HbA1c as detailed in **Appendix 14.6.3**.

6= Evaluate steatorrhea in the 4 weeks preceding the follow-up visit. Evaluate malnutrition risk level as per pre-albumin value.

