## 6.2. DOSE, ROUTE AND SCHEDULE OF INVESTIGATIONAL PRODUCT ADMINISTRATION

Patients will receive either reparixin at a dose of 2.772 mg/kg body weight/hour for 7 days (168 hrs) or matched (flow rate/length of infusion) placebo, according to the randomization number.

The dosing solution (if reparixin, 11mg/mL) will be administered as a continuous i.v. infusion into a (high flow) central vein, by an infusion pump adequate to provide reliable infusion rates (see below), as per treatment schedule.

Infusion of the Investigational Product will start approximately 12hrs (allowed range 6-18hrs) before the anticipated time when islet infusion is started. The Investigator will identify the time to start study drug administration.

The pump rate will be adjusted to provide an infusion rate of approximately 0.25mL/kg/hour. Actual infusion rate (mL/hour), adjusted to body weight, is tabulated in [Appendix 14.3](#). Figures in the appendix represent mathematical rounding of original infusion rates derived from the following formula:

$$\text{Infusion rate (mL/hour)} = \frac{\text{dose (mg/kg/hour)} \times \text{body weight (kg)}}{11.00 \text{ mg/mL}}$$

Such a rounding affects actual administered dose/kg/hour by less than 1%.

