### 6.3.2. Criteria for discontinuation of Investigational Product

Phase 1 studies in patients with end stage renal disease have shown that renal function has a profound effect on plasma concentrations of a major, marginally active metabolite, carboxy-reparixin (DF2243Y), which was found to accumulate over time along with the increased elimination half-life. Even if toxicological results to date suggest that DF2243Y does not raise any safety concern, limited experience in humans recommends discontinuation of the drug in case of renal impairment as it would not be possible to predict the risk associated with elevated plasma levels.

Because reparixin undergoes extensive hepatic metabolism, hepatic dysfunction should also be monitored to avoid an increase in plasma levels. An asymptomatic, self-limited transaminitis is consistently seen after islet transplantation into the liver. This is characterized by elevation in AST/ALT which peaks at about 7 days post transplant and spontaneously normalizes within 4 weeks. Bilirubin and other liver function tests remained within the normal range, suggesting no major hepatic dysfunction that would impact reparixin metabolism. [Rafael, 2003; Barshes, 2005].

Therefore, the Investigational Product should be immediately discontinued in case the patient develops renal or hepatic dysfunction defined as:

**Renal dysfunction:** the occurrence of both CLcr < 60 mL/min **and** urine output < 0.5 mL/kg/hour on two consecutive samplings. Transient alterations of serum creatinine or urine output, other than defined above, do not indicate a renal dysfunction that would cause impaired excretion of DF2243Y.

**Hepatic dysfunction:** the occurrence of ALT/AST > 3 x ULN **and** total bilirubin > 3mg/dL [> 51.3 µmol/L].

Renal and hepatic function will be evaluated daily from post-operative day 1 during Investigational Product infusion. Samples will be processed immediately and results made available as soon as possible to the Investigator.

Additionally, the Investigational Product should be immediately discontinued in the event of any other possibly drug related occurrences that the Investigator believes might compromise patient safety.

Lastly, the Investigational Product will be immediately discontinued in the case the patient withdraw his/her consent or has not received the transplant.

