#### 7.1.2. Start of infusion with the Investigational Product

Infusion of the Investigational Product will start approximately 12hrs (6-18hrs) before the anticipated time of islet infusion. The Investigator will identify the time to start study drug infusion. Infusion may be halted during pancreatic surgery if required, provided that interruption is not longer than 6 hours.

The infusion pump will be set to provide the infusion rate corresponding to the planned dose. Infusion rate (mL/hour) corresponding to each unit increment (kg) of body weight, is reported in **Appendix 14.3**.

Immediately before the start of infusion, the removable label on the Infusion Bag No. 1 will be detached and attached to the relevant page of the CRF. Starting time of drug administration and infusion rate will be recorded in the CRF.

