#### **7.1.4. Drug administration during hospital stay**

Administration of the Investigational Product will continue during hospital stay.

Infusion Bags will be used in a sequential manner (No. 1, No. 2, No. 3 etc.) and infusion of the Investigational Product will progress non-stop up to a total of 7 day (168hrs) administration.

The removable label on each new Infusion Bag will be detached and attached to the relevant page of the CRF. Start date/time and stop date/time for each Bag will be recorded in the CRF, along with accidental interruptions of study drug infusion for > 30min (cumulative within each 24 hours).

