#### **7.1.5. Post-operative assessments**

The following will be assessed during hospital stay and recorded in the CRF. Measurement will be performed as per centre practice, unless otherwise specified.

- Renal function (Clcr, urine output): Renal function will be assessed daily from post-operative day 1 up to the end of study drug infusion. Details of Clcr calculation are reported in **Appendix 14.6.2**. There is no need to have a urine catheter in place, if this is not required by standard of care. Urine volume will be measured at urination (measuring cylinder); corresponding collection time will be calculated from the previous urination. Depending from feasibility and patient compliance, ideally more than one measurement should be done over a 24-hour period to get the best estimate of urine output.
- Total bilirubin: Total bilirubin will be assessed daily from post-operative day 1 up to the end of study drug infusion as part of hepatic function evaluation.
- XDP, ALT/AST, INR/PTT, C-reactive protein (CRP): These will be measured daily from day 1 up to day 7 post-transplant.
- Chemokines/cytokines [CXCL8, CCL2 (MCP-1), CCL3, CCL4, CXCL10 (IP-10), CXCL9 (MIG), IL-6, IL-10, INF- $\gamma$ , TNF- $\alpha$ , and IL-1 $\beta$ ]: A blood sample will be obtained @ 6, 12, 24, 72, 120 and 168hrs after the end of islet infusion. Samples will be handled and stored for the centralized assay, as detailed in **Appendix 14.6.3**.
- miR-375: A blood sample will be obtained @ 6, 12, 24, 72, 120 and 168hrs after the end of islet infusion. Samples will be handled and stored for the centralized assay, as detailed in **Appendix 14.6.3**.
- Pharmacokinetics [plasma levels of reparixin (total and unbound) and relevant metabolites (DF2243Y and ibuprofen)]: A blood sample will be obtained in all patients randomized and treated with the Investigational product on post-operative day 1, 3 and 5, ideally in the morning. In a subset of at least 20-24 patients, treated at 2 selected sites, a blood sample will be also obtained just prior to, and then at 1, 3, 5, 6, 8, and 12 hrs after termination of Investigational Product administration. Samples will be handled and stored for centralized assay, as detailed in **Appendix 14.6.3**.
- Safety laboratory tests: Laboratory tests will be performed before hospital discharge.
- Vital signs, i.e. blood pressure (BP) and heart rate (HR) will be measured before hospital discharge.

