**14.5. APPENDIX 5 - ACCEPTABLE TIME WINDOWS FOR ASSESSMENTS/ PROCEDURES**

Assessment/Procedure	Window
Investigational Product administration	
Start of Investigational Product infusion @ 12hrs prior to islet transplant.	6-18hrs prior to start of islet infusion
End of Infusion @ 7 days (168hrs).	± 12hrs
Follow-up visits	
Visit @ day 75 and 365 after the transplant	± 14 days
Mixed Meal Tolerance Test	
Sampling @ 15, 30, 60, 90, 120, 180, 240 mins after the meal	± 5 mins (15 min and 30 min) or ± 10 mins (60 to 240 min)
Chemokine/cytokines; miR-375	
Sampling @ 6, 12, 24, 72, 120 and 168hrs after islet infusion	± 10 mins (6 to 24 hrs) or ± 30 mins (72 to 168hrs)
PK sampling	
Sampling on post-operative day 1, 3 and 5, ideally in the morning	Between 5.30 a.m. and 12.30 p.m.
Sampling just prior to termination of Investigational Product administration	Within 6 hrs before the end of Investigational Product administration
Sampling @ 1, 3, 5, 6, 8, and 12 hrs after termination of Investigational Product administration	± 10 mins

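### The flow chart schedules renal checks only to day 6 post-transplant, while sections 6.3.2 and 7.1.5 require them daily to the end of an infusion that can run into day 7; the passages must be reconciled

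*Protocol*

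**What the plan says.** Three places in the protocol set the renal monitoring schedule.

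- Appendix 4 (section 14.4), flow chart footnote 2: "Assess creatinine clearance AND urine output from day 1 to day 6 post-transplant".
- Section 7.1.5: "Renal function will be assessed daily from post-operative day 1 up to the end of study drug infusion".
- Section 6.3.2: "Renal and hepatic function will be evaluated daily from post-operative day 1 during Investigational Product infusion".

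Section 6.3.2 also holds the stopping rule that these checks serve. Renal dysfunction requires both a creatinine clearance below 60 mL/min and "urine output < 0.5 mL/kg/hour on two consecutive samplings".

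On timing, section 6.2 states: "Infusion of the Investigational Product will start approximately 12hrs (allowed range 6-18hrs) before the anticipated time when islet infusion is started". Section 7.1.4 adds that "infusion of the Investigational Product will progress non-stop up to a total of 7 day (168hrs) administration". Appendix 5 allows the end of infusion to vary by ±12 h around 168 h. Section 7.1.2 permits a pause: "Infusion may be halted during pancreatic surgery if required, provided that interruption is not longer than 6 hours".

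The opening of section 7 sends sites to the flow chart for the schedule of tests. No clause says whether the chart or the body text prevails when they differ.

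**The concern.** The chart fixes the last renal check to a calendar day, whereas the body text ties it to an event, the end of infusion. The two agree only if the infusion always ends by day 6, and the protocol's own timing does not ensure that.

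The stake is the renal stopping rule. Section 6.3.2 explains that the metabolite DF2243Y accumulates when renal function is poor, and that the risk of raised levels cannot be predicted from the limited human experience. A site working from the chart would have no scheduled renal check during any infusion on day 7. It would also have no scheduled second sampling if the two criteria were first met on day 6.

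**Working it through.** **Inputs**

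- Length of infusion: 7 × 24 = 168 h, which reproduces the protocol's figure (sections 6.2 and 7.1.4).
- Lead before islet infusion: about 12 h, range 6-18 h (section 6.2).
- End window: ±12 h (Appendix 5).
- Surgical halt: up to 6 h (section 7.1.2). The protocol does not say clearly whether halted time is made up at the end.
- Day 0: the calendar date of islet infusion (SAP section 5). Day 7 therefore begins 168 h after 00:00 on day 0.
- Clock time of islet infusion: not given. Section 7.1.3 says only that it is on the same day as the pancreatectomy.

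**Step 1: when the infusion ends**

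End, in hours after islet infusion = 168 − lead.

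- 6 h lead: 168 − 6 = 162 h
- 12 h lead: 168 − 12 = 156 h
- 18 h lead: 168 − 18 = 150 h

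With the window, the range is 150 − 12 = 138 h to 162 + 12 = 174 h. If a 6 h halt is made up, the upper limit is 174 + 6 = 180 h.

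**Step 2: which calendar day that is**

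With no halt and no use of the window, the infusion reaches day 7 when clock time + 168 − lead ≥ 168, that is, when clock time (in hours) ≥ lead. The thresholds are 06:00, 12:00 and 18:00 for leads of 6, 12 and 18 h. Two examples at a 12 h lead: islets at 10:00 give an end at 22:00 on day 6, and islets at 16:00 give an end at 04:00 on day 7.

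**Step 3: sensitivity to the missing clock time**

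Assume the islet clock time T is uniform over the stated window, the lead L is uniform over 6-18 h, and a renal sample is drawn at 08:00 each day. All of these are assumptions. The ±12 h window is not used.

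| Islet infusion | Ends on day 7, no halt | Ends on day 7, 6 h halt made up | Mean hours from 08:00 on day 6 to end, no halt | 08:00 draw on day 7 precedes end, no halt |
|---|---|---|---|---|
| 10:00-16:00 | 58% | 97% | 17 | 3% |
| 12:00-20:00 | 81% | 100% | 20 | 19% |
| 14:00-22:00 | 92% | 100% | 22 | 33% |

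- Ends on day 7, no halt: P(T ≥ L). First row: (13 − 6)/12 = 0.58. Second: (6 × 0.75 + 2 × 1)/8 = 0.81. Third: (4 × 0.833 + 4 × 1)/8 = 0.92.
- Ends on day 7 with the halt made up: P(T ≥ L − 6). In the first row this fails for 2/72 = 3% of combinations.
- Mean hours: mean T + 168 − 12 − 152, where 152 h is 08:00 on day 6. This gives 13 + 4 = 17, 16 + 4 = 20 and 18 + 4 = 22.
- Last column: P(T − L ≥ 8) = 2/72, 18/96 and 32/96.

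**Step 4: how much of the gap comes from the footnote**

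In 67%-97% of these no-halt combinations, an 08:00 draw on day 7 would come after the infusion had ended. There, a once-daily schedule that follows the body text leaves the same interval after the day 6 draw as the chart does. Most of the 17-22 h is therefore the ordinary interval after a once-daily sample.

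**Step 5: the two-sampling rule against the chart**

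If both criteria are first met on day 6, the chart offers no later renal sampling. Section 6.3.2 asks for two consecutive samplings without a minimum interval. Section 7.1.5 encourages more than one urine measurement in 24 h; it gives no such advice for creatinine clearance, and renal function as a whole is assessed daily. A repeat is therefore possible but not scheduled.

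**The case against.** The best defence is that two body sections agree with each other and only a chart footnote differs, so a careful site would monitor to the end of infusion anyway. That is fair, and it limits the consequence to sites that work from the chart. It does not remove the conflict, because section 7 names the chart as the place to find the schedule and nothing ranks the texts.

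Four stronger readings are tempting, and the documents do not support them.

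- A reader might infer that the stopping rule goes unapplied in the last hours of dosing. Sections 6.3.2 and 7.1.5 both require the checks, so this would happen only where a site follows the footnote against them.
- A reader might infer that a first positive result on day 6 could never be confirmed. The rule counts samplings, not days, and sets no minimum interval. Section 6.3.2 also provides for discontinuation on other possibly drug-related safety grounds.
- A reader might infer that infusion usually ends on day 7. That is plausible after same-day pancreatectomy and islet isolation, but it depends on clock times the documents do not give. The end window also works in both directions and can bring the end forward to 138 h.
- A reader might take the 17-22 h after a day 6 morning draw (10%-13% of 168 h) as infusion time left unmonitored because of the footnote. Step 4 shows that most of it would remain under a once-daily schedule that follows the body text.

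**Conclusion.** The inconsistency is real and rests on the wording alone. Footnote 2 stops at day 6, and sections 6.3.2 and 7.1.5 run to the end of infusion. In the extracted chart the row for renal function and total bilirubin also has only six post-transplant marks, but its column positions are unreliable, so the footnote is the firm evidence.

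The nominal end is 150-162 h after islet infusion (138-174 h with the window), which puts it on late day 6 or on day 7 according to an unstated clock time. The 58%-92% shares illustrate that day 7 infusion is a realistic possibility under the assumed islet times and leads. They do not estimate what happened in the trial. The hours in the table should not be used as a measure of harm.

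Because a drug-stopping rule depends on this schedule, the point is more than clerical and should be corrected.

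**What to change.** Reconcile footnote 2 and the renal function row of the flow chart with sections 6.3.2 and 7.1.5, so that the protocol states one renal monitoring schedule. Check that schedule against the two-sampling requirement in section 6.3.2. Which schedule stands is for the sponsor to decide.

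Changing one day mark in the chart may not by itself settle the matter, since a fixed morning sample on day 7 would often fall after the infusion has ended (last column of the table).

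The document change is small: one footnote and one chart row, or the matching sentences in the two sections. Whether CRF pages need to change cannot be judged, because they are not among the documents. The amendment that raised the enrolment cap reports 86 patients transplanted against a goal of 100, so at that point a correction could still have applied to the remaining patients.
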